#### **Microbiological Response**

**Eradication or presumed eradication:** Baseline pathogen not isolated from original site culture(s), or culture data are not available for a subject with successful clinical outcome.

**Persistence (documented or presumed):** Any baseline *Candida* sp. is present in repeat cultures, or culture data are not available for subject with a clinical outcome of failure.

**Indeterminate:** Culture data are not available for a subject with a clinical outcome of indeterminate.

### 6.1.2. Global Response at the End of all Treatment (EOT)

Global response at EOT will be programmatically determined utilizing the same global response, clinical response and microbiologic response definitions for EOIVT, described in [Section 6.1.1.1](#) and [Section 6.1.1.2](#).

A global response determination of failure at EOT will be carried forward programmatically to all subsequent visits.

### 6.1.3. Global Response at the 2 and 6 Week Follow-Up Visits

Global response at the 2 and 6 Week Follow-up Visits will be programmatically determined utilizing the same global response definition described in [Section 6.1.1.1](#).

Clinical and microbiologic definitions to be used for programmatic global response determination at the 2 and 6 Week Follow-Up Visits are as follows:

#### **Clinical Response**

**Cure:** Resolution of sign and symptoms attributed to *Candida* infection; no additional systemic or oral antifungal treatment required to complete the course of therapy.

**Improvement:** Significant, but incomplete resolution of signs and symptoms of the *Candida* infection; no additional systemic or oral antifungal treatment required to complete the course of therapy.

#### ***Important Notes:***

- Initiating or resuming oral antifungal therapy following EOT for prophylactic purposes is permitted, and does not reflect a requirement for additional systemic antifungal therapy for treatment purposes, and therefore does not constitute treatment failure. (Note: It must be clear in the project database that administration of additional antifungal therapy is for prophylactic purposes, otherwise it will be deemed as being administered for treatment of continued infection, in which case study drug treatment will be considered clinical failure). Thus, use of oral prophylactic antifungal therapy following EOT does not constitute treatment failure.
- Administration of non-absorbable antifungal agent is not considered systemic antifungal treatment in the context of this study.

**Failure:** No significant improvement in signs and symptoms, or death due to the *Candida* infection. Subjects must have received at least 3 doses of study medication to be classified as a failure.

**Indeterminate:** Evaluation cannot be made to withdrawal from the study prior to assessment of cure or failure. Subjects who receive fewer than 3 doses of study medication will be assigned as a clinical efficacy response of indeterminate.

### **Microbiological Response**

**Eradication or presumed eradication:** Baseline pathogen not isolated from original site culture(s), or culture data are not available for a subject with successful clinical outcome.

**Persistence (documented or presumed):** Any baseline *Candida* sp. is present in repeat cultures, or culture data are not available for subject with a clinical outcome of failure.

**Indeterminate:** Culture data are not available for a subject with a clinical outcome of indeterminate.

**Relapse (recurrence):** Any baseline *Candida* sp. isolated following eradication (documented or presumed); or culture data are not available for a subject with a clinical response of failure after a previous response of success; prophylactic treatment with oral antifungal agents is not sufficient to document a relapse.

**New Infection:** Subject presenting with clinical failure with the emergence of new *Candida* sp. at the original site of infection or at a distant site of infection;

A global response determination of failure at the 2 Week Follow Up will be carried forward programmatically to all subsequent visits.

#### **6.1.4. Concomitant Antifungal Therapy**

Global response at EOIVT, EOT, 2 and 6 Week Follow up will be set to failure following the use of a concomitant medication with activity for any baseline *Candida* spp., based on the following algorithm for handling the global response,

- If a subject takes two or more days of antifungal medications (as identified by the clinical team) after the start of study medication until the end of treatment for any reason, they are imputed to failure for all visits that occur after the antifungal medication was taken.
- If a subject takes one day of antifungal medication after the start of study medication until the end of treatment for the reason “lack of efficacy” they are similarly imputed to failure for all visits that occur after the antifungal medication was taken. The clinical team will determine whether the antifungal medication has been used for “lack of efficacy”.

- In the FU period, if a subject takes at least one day of antifungal medication for reason of “lack of efficacy”, they are imputed to failure for all visits that occur after the antifungal medication was taken. Again, the clinical team will determine whether the antifungal medication has been used for “lack of efficacy”.

### **6.1.5. Rate of Response Based on Clinical Cure and Microbiological Success at EOIVT, EOT, 2 and 6 Week Follow-Up Visits**

The rate of response will be reported as a subset of subjects who have a global response of success which will be defined as subject with clinical cure and microbiologic eradication or presumed eradication.

#### **6.1.5.1. Rate of Relapse at the 2 and 6 Week Follow-Up Visits**

The rate of relapse, defined as a microbiologic response of relapse, at the 2 and 6 Week Follow-Up Visit will be reported.

#### **6.1.5.2. Rate of New Infection at the 2 and 6 Week Follow-Up Visits**

The rate of new infection, defined as a microbiologic response of new infection, at the 2 and 6 Week Follow-Up Visit will be reported.

#### **6.1.5.3. All-Cause Mortality During Study Therapy and Follow-Up Visits**

The mortality rate at EOIVT, EOT, 2 week and 6 week follow-up will be calculated as the proportion of subjects who died by these timepoints in the trial, based on the number of subjects in the study population at the start of the trial.

#### **6.1.5.4. Time to Death**

For this analysis, time to death will be measured from the first dose of study medication in days. For subjects who died, time to death is defined as:

$$T = \text{date of death} - \text{first treatment date} + 1$$

where date of death will be recorded on the End of Study page and/or Infection Notice of Death page. These observations will be regarded as events for the purposes of time to event analyses.

Subjects who are not known to have died, will be censored at their last known survival date taken as the latest date in the database. Time to death is defined as:

$$T = \text{latest date in the database} - \text{first treatment date} + 1$$

where the latest date is expected to be the date of the End of Study visit.

## **6.2. Safety Endpoints**

The safety assessment is the primary endpoint of the study. The following safety assessments will be performed:

### **6.2.1. Adverse events**

Any events occurring following start of treatment or increasing in severity will be counted as treatment emergent.

For the standard required analysis, events that occur in a non-treatment period (up to 30 days after last dose of study drug) will be counted as treatment emergent and attributed to the previous treatment taken.

### **6.2.2. Laboratory Tests**

Hematology and blood chemistry will be performed by the local laboratory at all visits according to the protocol.

To determine if there are any clinically significant laboratory abnormalities, the hematological and clinical biochemistry safety tests will be assessed against the criteria specified in the sponsor reporting standards. The assessment will take into account whether each subject's baseline test result is within or outside the laboratory reference range for the particular laboratory parameter.

### **6.2.3. Physical Examination and vital signs**

- A complete physical examination (including vital signs) at Screening;
- A targeted physical examination on Days 3, 7, 10, 11-34 (every 3 days), EOIVT, EOT, Week 2 FU visit, and Week 6 FU visit.

The number of subjects whose physical examination significantly changed from the previous physical examination will be assessed for each visit.

- Vital signs (including temperature) at Screening, daily through EOT, Week 2 FU visit, and Week 6 FU visit.

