## 8.3. Definition of an Adverse Event

An adverse event is any untoward medical occurrence in a clinical investigation subject administered a product or medical device; the event need not necessarily have a causal relationship with the treatment or usage. Examples of adverse events include but are not limited to:

- Abnormal test findings;
- Clinically significant symptoms and signs;
- Changes in physical examination findings;
- Hypersensitivity;
- Progression/worsening of underlying disease;
- Drug abuse;
- Drug dependency.

Additionally, they may include the signs or symptoms resulting from:

- Drug overdose;
- Drug withdrawal;
- Drug misuse;

- Drug interactions;
- Extravasation;
- Exposure during pregnancy (EDP);
- Exposure via breast feeding;
- Medication error;
- Occupational exposure

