### **9.1. Analysis of Primary Endpoint**

The primary analysis will be the evaluation of adverse events throughout the trial, laboratory tests, and physical examination.

The set of subjects for this evaluation will be the Safety population, defined as all subjects with at least 1 dose of study medication.

The following parameters will be summarized: rates of discontinuation, adverse events, ECG findings (if applicable), and laboratory abnormalities.

The Sponsor has standard algorithms for reporting adverse events and clinical laboratory test results, and these will be employed in the analysis of the data from this trial. Safety data will be subject to clinical review and summarized by appropriate descriptive statistics. Descriptive statistics for categorical data will include frequencies and/or percentages.

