### 8.2.1. Primary Analysis

The primary analysis is to examine safety and tolerability of anidulafungin. The set of subjects for this evaluation will be the Safety population. The following parameters will be summarized: rates of discontinuation, adverse events, visual tests, physical examination, ECG findings (if applicable), and laboratory abnormalities. The analysis methods are described in [Section 8.2.4](#).

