#### **8.2.4.9. Physical Examination and Vital Signs**

All physical examination and vital sign data will be provided in the listings.

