Frequency Table of Fundoscopy Changes - Left Eye
Duration of Treatment - Treatment Regimen - Safety Population
Duration of Treatment - Combined Treatments - Safety Population
Duration of Treatment - Treatment Regimen - MITT Population
Duration of Treatment - Combined Treatments - MITT Population
Drug Treatments Prior to Start of Study Treatment - Safety Population
Drug Treatments During Study Treatment - Safety Population
Drug Treatments During Study Treatment - MITT Population
Drug Treatments After Study Treatment - Safety Population
Drug Treatments After Study Treatment - MITT Population
Nondrug Treatment Prior to Study Treatment
Nondrug Treatment During Study Treatment
Summary of Exclusions from MITT Population
Listings
Randomization listing
Subject Evaluation Groups
Subject Discontinuations from Study
Subject Discontinuations from Treatment
Protocol Deviations
Inclusion/Exclusion from Analysis Populations
Demographic Characteristics
Primary Diagnoses and Duration
Medical History
Drug Treatments Prior to the Start of Study Treatment
Nondrug Treatments Prior to Start of Study Treatment
Administration Schedule
Antifungal Drug Treatments
Concomitant Drug Treatments
Concomitant Nondrug Treatments
Study Treatment Compliance for Outpatient Fluconazole Treatment
[PKBDFLD] [PKTERM] Concentration ([PKCNCU]) versus Time Listing - All Age Groups
Site of Infection
Response Listing
Signs and Symptoms of Invasive Candidiasis
Microbiology Data (Local data)
Microbiology Data (Vendor data)
Histopathology/Cytology data (Local data)
Candidemia Risk Factors
Candida Osteomyelitis MRI Findings
Candida Endocarditis Echocardiogram Findings - Follow-up Assessment
Candida Endocarditis Echocardiogram Findings - Full Assessment
Adverse Events
Adverse Events (Treatment Related)
Listing of Treatment-Emergent Adverse Events – By Risk - Safety Subjects

Laboratory Data
Laboratory Test Abnormalities, by Subject
Laboratory Test Abnormalities, by Test
Vitals Signs Data
Vital Signs Change from Baseline
Electrocardiogram Data (Local data)
Electrocardiogram Data (Reference Laboratory)
Physical Examination Findings at Baseline
Physical Examination: Changes from Screening
Fundoscopy and Fundoscopy Change
Medication Error Listing
Radiographic Assessment
Intravenous Catheter Details at Baseline
Deaths (Source: Project Database)
Investigator Comments
Safety Narratives- (one output per usubid)
Figures
Kaplan-Meier Plot of Time to Death - Safety Population

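### The SAP's physical-examination count has no direction and a moving reference, so it cannot separate deterioration from recovery, and the SAP sections that report it disagree.

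*SAP*

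**What the plan says.** Safety is primary: SAP 6.2 states "The safety assessment is the primary endpoint of the study", and Protocol 9.1 states "The primary analysis will be the evaluation of adverse events throughout the trial, laboratory tests, and physical examination".

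SAP 6.2.3 sets a complete examination at Screening and then "A targeted physical examination on Days 3, 7, 10, 11-34 (every 3 days), EOIVT, EOT, Week 2 FU visit, and Week 6 FU visit". Its counting rule is "The number of subjects whose physical examination significantly changed from the previous physical examination will be assessed for each visit". Neither document defines a significant change for this purpose, limits the count to worsening, or splits it by direction.

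Three other places in the SAP deal with the output:

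- 8.2.1 (Primary Analysis): "The following parameters will be summarized: rates of discontinuation, adverse events, visual tests, physical examination, ECG findings (if applicable), and laboratory abnormalities".
- 8.2.4.9, the section specific to this measure: "All physical examination and vital sign data will be provided in the listings". No table is planned there.
- Appendix 2 includes a listing titled "Physical Examination: Changes from Screening". By SAP 3.1, that appendix covers the interim analysis of the 2 to <5 and 5 to <18 years cohorts.

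Protocol 8.3 gives "Changes in physical examination findings" as an example of an adverse event. SAP 6.2.1 treats events as treatment emergent when they start after treatment begins or become more severe.

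**The concern.** A safety count should rise when subjects get worse. This one rises when they change either way, then falls back when they stop changing, even if they remain worse. A reader of the study report could take a high count at one visit as a safety signal when it reflects recovery, or take a later zero as resolution when the deterioration persists.

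The SAP treats its other safety data more carefully. Adverse events have a direction (6.2.1). Laboratory abnormalities are judged with regard to the subject's baseline (6.2.2), and laboratory changes are summarized from baseline (8.2.4.6). Physical examination has neither safeguard.

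The conflict between sections adds to this. A programmer cannot tell from the SAP whether a table is required or only a listing, nor whether the reference is the previous examination or Screening. For children aged 1 month to <2 years, the SAP specifies no output that uses Screening as the reference.

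**Working it through.** The plan states no figure to reproduce. The check applies the SAP 6.2.3 rule literally to assumed examination sequences.

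**Inputs.** The visits are Screening, Day 3, Day 7, Day 10, EOIVT, EOT, Week 2 FU and Week 6 FU (SAP 6.2.3). The three-day visits in Days 11–34 are left out for simplicity, which leaves 7 post-screening visits. Assumed coding: s = 0 for normal, 1 for abnormal, and any switch is significant.

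**Formulas, per subject at visit v.**

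- SAP rule: counted if s(v) ≠ s(v−1).
- Directional comparison: counted if s(v) > s(Screening).

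**Single-subject patterns, Day 3 to Week 6 FU.**

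| Assumed pattern | SAP rule | Visits counted | Worse than Screening | Visits worse |
|---|---|---|---|---|
| Lasting deterioration from Day 7 | 0,1,0,0,0,0,0 | 1 | 0,1,1,1,1,1,1 | 6 |
| Lasting recovery at Day 7 | 0,1,0,0,0,0,0 | 1 | 0,0,0,0,0,0,0 | 0 |
| Worse at Day 7, back to normal at Day 10 | 0,1,1,0,0,0,0 | 2 | 0,1,0,0,0,0,0 | 1 |

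Under the SAP rule the first two rows are identical. The lasting deterioration is counted at 1 visit and at 0 of the 5 later ones, although the subject is worse than Screening at 6 of 7. The transient worsening is counted twice, more often than the lasting one.

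**Group illustration: 30 subjects change at Day 7 and stay changed.**

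| Deteriorated / recovered | SAP count, Day 7 | SAP count, each later visit | Worse than Screening, Day 7 and each later visit |
|---|---|---|---|
| 0 / 30 | 30 | 0 | 0 |
| 5 / 25 | 30 | 0 | 5 |
| 15 / 15 | 30 | 0 | 15 |
| 25 / 5 | 30 | 0 | 25 |
| 30 / 0 | 30 | 0 | 30 |

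The SAP count is the same in every row, while the number of subjects who are worse runs from 0 to 30.

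**Limit of the pattern.** The drop-out after one visit belongs to a one-step deterioration. On a finer scale, a child who takes a significant step down at each of Days 3, 7 and 10 is counted at 3 visits.

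**Sections side by side.** SAP 6.2.3 gives a count per visit against the previous examination. SAP 8.2.1 gives a summary with no reference stated. SAP 8.2.4.9 gives listings only. Appendix 2 gives a listing against Screening, for the interim analysis in two of the three age groups. A programmer who followed 8.2.4.9 alone would not deliver what 6.2.3 and 8.2.1 promise.

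**The case against.** The strongest reply is that harm is captured elsewhere, and with a direction. Examination changes can be reported as adverse events (Protocol 8.3). Treatment-emergent events are restricted to new or worsening ones (SAP 6.2.1). They are tabulated by system organ class, preferred term, age category and severity, with all-causality and treatment-related versions (SAP 8.2.4.5). This stands, and it limits the consequence. It does not make the count interpretable.

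Second, the count may never be produced. Section 6 says it only defines endpoints and leaves analysis to Section 8, where 8.2.4.9 plans listings. Appendix 2 has no examination table. But 8.2.1 says examination will be summarized, and 8.2.4 says the 6.2 endpoints will be listed and summarized under sponsor standards that are not in these documents. The objection therefore confirms the conflict and does not remove the defect.

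Third, Screening is not a perfect reference. Protocol 7.2 describes a complete examination at Screening and abbreviated, focused ones later. This stands, and the fix allows for it.

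A reader might also infer that the counts will consist mainly of recoveries, and try to size this from the 75.6% success rate in the adult trial (Protocol 1.3.2). The documents do not support that:

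- The 75.6% is a global response at EOIVT that combines clinical and microbiological outcome. It is not a rate at which examinations normalise.
- No document gives the share of children abnormal on examination at Screening. Confirmed cases need at least one clinical criterion (Protocol 4.1), but some of those criteria are laboratory findings, and the high-risk infants need none.
- The planned 60 are evaluable, Candida-confirmed subjects, not the Safety population in which examination is analysed.
- A gradual recovery made of small steps would escape the rule just as a gradual worsening would.

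**Conclusion.** The point holds as a defect in a stated rule for a component of the primary safety analysis, together with a conflict between SAP 6.2.3 and 8.2.1 on one side and 8.2.4.9 and Appendix 2 on the other. The count cannot separate deterioration from recovery, and it drops a sustained one-step deterioration after its first visit. This rests on reading 6.2.3 literally and on there being no definition of a significant change elsewhere in the documents. The numbers in the working are illustrations. The documents give no basis for estimating how many subjects would be affected.

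It would go too far to infer that the measure misses harm altogether, or that the trial's safety conclusion is compromised. New deteriorations do enter the count, stepwise ones can enter more than once, and adverse-event reporting offers a directional route to the same findings. The effect on the overall safety conclusion is limited. The correction is still worth making before the final analysis, because the examination count cannot be interpreted as it stands.

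**What to change.** In SAP 6.2.3, replace the count with the number and percentage of subjects with a clinically significant worsening from Screening/Baseline, by visit and at any post-baseline visit. Show improved and unchanged separately, and state what makes a change clinically significant.

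Add the table to SAP 8.2.4.9, by age category, in the Safety population. Bring 8.2.1 and Appendix 2 into line, so that one reference and one form of output apply throughout and the youngest age group is covered.

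Limit the comparison to body systems examined at both Screening and the visit concerned, because later examinations are targeted. Use subjects with such a pair of examinations as the denominator at each visit.

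The cost is SAP wording and one extra table, with no change to trial conduct. The table assumes that the CRF, which is not among these documents, records enough to classify direction and clinical significance. If it does not, the recorded findings would need a documented clinical review first.

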### **6.2.4. Fundoscopic Examination**

The fundoscopic examination assessment results are reported as normal/abnormal or present/absent at Screening for each eye and at EOIVT, EOT, Week 2 FU visit, and Week 6 FU visit if the Screening fundoscopic examination is positive for endophthalmitis. The Screening visit data will be summarized for all subjects.

## **6.3. OTHER Endpoints**

There are no other endpoints planned for this study.

## **6.4. Covariates**

As this is a descriptive study, there are no covariates needed for this study.

As an objective of the study is to examine safety and efficacy within the different age groups, a number of the variables will be presented split into the age categories: 1 month - <2 years, 2 years - <5 years and 5 - <18 years.

Global response rates for each of the different *Candida* species will also be reported.

Site of infection is of interest to see whether there are different response rates dependent on the site of infection. Global response rates will be presented for each of the three categorizations for rate of response:

- i. Blood only;
- ii. Blood and other sterile site;
- iii. Sterile site (other than blood) only.

Dependent on numbers of subjects, global response may also be presented by different underlying diseases.

- neutropenic status (<500 neutrophils vs  $\geq$ 500 neutrophils.)
- allogeneic BMT vs not allogeneic BMT

## 7. HANDLING OF MISSING VALUES

For global response, missing values are treated as failures. Sensitivity analyses will also be performed in which subjects with missing values for global response are excluded from the analysis.

For the analysis of safety endpoints, the sponsor data standard rules for imputation will be applied.

